2 INTRODUCTION

2.1 STUDY RATIONALE

Acute heart failure (AHF) is a common discharge diagnosis in the emergency department (ED), associated with 1-month mortality of 6%, and a 30% risk rate of 1-month rehospitalization (Metra et al., 2019; Arrigo et al., 2020). AHF is also associated with a high risk of early worsening clinical state, with a reported rate of 10-14% at day 7 (Cannon et al., 2015; Cotter et al., 2008). Current guidelines recommend the use of nitrates and low dose diuretic to treat congestion, but to date, no drug has ever shown any improved clinical outcome when given at the acute phase (Mebazaa et al., 2015).

Several studies suggest that there is a high inflammatory component in AHF (Goonewardena et al, 2016), with elevated markers such as IL6 and C-reactive protein (CRP). As it is the case in other acute respiratory disease, a short course of steroid therapy may limit the inflammatory response and in turn, improve AHF prognosis.

The objective of the study is to assess the effect of a 7-day course of steroid introduced in the ED or early in the hospitalization on inflammatory response.

2.2 BACKGROUND

The lack of clinical benefit of current recommendations was confirmed in the recent ELISABETH RCT that included 503 patients aged > 75 years in 15 EDs in France. In this trial, the overall 1 month mortality of patients aged > 75 years after AHF was 10%, with a mean of 16 days alive and out of hospital at day 30 (Freund et al, 2020).

Several markers of inflammation such as CRP, IL6 or monocytes are reportedly higher in patients with AHF than in healthy subjects. Furthermore, studies report an association between inflammatory markers (IL6 and CRP) and worse prognosis (Kalogeropoulos et al, 2014; Davison et al, 2021). A doubling of IL6 level was associated with an increased risk of hospital admission (OR 1.31 [1.11 – 1.61]) and increased death at 180 days (OR 1.33 [1.15 – 1.54]) and patients that had a persistent elevated CRP at 30 days are reportedly at higher risk of death (OR 2.29 [1.16 – 4.52]).

Preliminary studies have suggested that a short course (7 days) of low dose (40 mg) steroids therapy (burst) may help improve prognosis in patients with heart failure partially because a potent diuretic effect (Liu, Zhao et al, 2016; Liu, Ge et al, 2016; Liu et al 2007). Usual recommended dose is 40 mg of prednisone or its equivalent (6mg dexamethasone), for a 5 to 7 days period. An early short course of steroid (prednisone or dexamethasone) have been proved to improve short term prognosis in patients with acute respiratory disease such as chronic obstructive pulmonary disease exacerbation, asthma or COVID-19 (Le Conte et al, 2019; Wedzicha et al., 2017; The RECOVERY Collaborative Group, 2021). This early treatment is reportedly associated with side effects such as sepsis, thromboembolic event and fracture, with a global risk of less than 2 per 1000 patients-years (Yao et al, 2020). Concerns were also raised about the potential detrimental effects of a short course of low dose steroids, which could be associated to a higher risk of heart failure exacerbations with an incidence rate of 1.3 per 1000 patients-years. However, this risk was limited in time and was attenuated after 30 days (Yao et al, 2020).

2.3 RISK/BENEFIT ASSESSMENT

2.3.1 Known Potential Risks

Steroid burst treatment (40mg during 7 days) has been reported to carry risk of fracture, thromboembolism event, gastro-intestinal bleeding and heart failure. However, these risks were reported as low with very low incidence (less than 2 per 1000 Persons years) [Yao et al, 2020; Burstin et al, 2002]. This treatment is reportedly associated with a global risk of less than 2 per 1000 patients-years,

with side effects that includes sepsis, thrombo-embolic event, and fracture. Steroids could also be associated to a higher risk of heart failure with an incidence rate of 1.3 per 1000 patients-years. However, this risk has been reported as limited in time and was attenuated after 30 days.

2.3.2 Known Potential Benefits

AHF carries an important mortality in the first month following ED visit (6% for all patients, and up to 10% in patients aged 75 years and over). The overall burden of AHF is high and also includes a high risk of return visit to the ED, rehospitalization and poorer quality of life.

If our hypothesis is confirmed, the CORTAHF study will be the first to suggest the efficacy of a simple and unexpensive treatment in patients with AHF that could reduce inflammation, which in turn could improve prognosis.

Furthermore, this pilot study would allow to have an estimation of the effect of this treatment and pave the way to the conduction of further phase 3 trials focused on clinical endpoints and larger validation studies, and the development and use of other anti-inflammatory agent in this indication.

3 OBJECTIVES AND ENDPOINTS

OBJECTIVES	ENDPOINTS	JUSTIFICATION FOR ENDPOINTS
Primary		
To assess the effects of prednisone therapy started in the ED and continued for up to 7 days on the change of CRP level	Change in CRP level at 7 days	CRP levels increase rapidly in response to trauma, inflammation and infection and decrease rapidly with resolution of these conditions (Du Clos 2000). Thus, CRP measurement is widely used to monitor inflammatory states.
Secondary		
To compare the effects on the occurrence of death, hospital readmission for HF or worsening HF (WHF) through day 91	The composite of first event of a WHF adverse event, hospital readmission for HF, or death through day 91	WHF has been shown to be associated with longer hospital stay and increased risk of HF readmission and death, and HF readmission and death are outcomes representing disease progression. The composite is a generally accepted endpoint in AHF trials. For this pilot study, the definition of WHF has been expanded to include all reported adverse events of WHF (not only those requiring intensification of IV therapy or mechanical support) over a broader timeframe (longer than 7 days).
To compare the effects on change in quality of life (QoL) as measured by the EQ-5D-5L questionnaire at day 7	Changes in quality of life measured by the EQ-5D-5L from randomization to day 7	Quality of life, encompassing functional capacity, psychological status, and frequent rehospitalizations may be particularly important to patients (Nieminen, Dickstein et al. 2015) The EQ-5D is a validated, standardized instrument developed by EuroQol.
Tertiary/Exploratory		

OBJECTIVES	ENDPOINTS	JUSTIFICATION FOR ENDPOINTS
To compare the effects on the occurrence of death, hospital readmission for HF or worsening HF (WHF) through day 31	The composite of WHF, death, or hospital readmission for decompensated HF at day 31. WHF is defined as worsening signs and/or symptoms of HF that require an intensification of intravenous therapy (including initiation or re-initiation or dose increase) for HF or mechanical ventilatory, renal or circulatory support (occurring between 24 hours after randomization and the earlier of discharge or day 7).	WHF has been shown to be associated with longer hospital stay and increased risk of HF readmission and death, and HF readmission and death are outcomes representing disease progression. The composite is a generally accepted endpoint in AHF trials.
To compare the effects on the occurrence of death, hospital readmission for HF or worsening HF (WHF) through day 91	The composite of WHF, death, or hospital readmission for decompensated HF at day 91. WHF is defined as worsening signs and/or symptoms of HF that require an intensification of intravenous therapy (including initiation or re-initiation or dose increase) for HF or mechanical ventilatory, renal or circulatory support (occurring between 24 hours after randomization and the earlier of discharge or day 7).	HF readmission and death are outcomes representing disease progression. The composite is a generally accepted endpoint in AHF trials.
To compare the effects on change in quality of life (QoL) as measured by the EQ-5D-5L questionnaire at day 31	Changes in quality of life measured by the EQ-5D-5L from randomization to day 31	To explore longer-term effect on quality of life.
To compare the effects on symptoms and signs of heart failure at day 7 including weight	Changes from randomization to day 7 in: 
 • NYHA classification, • orthopnea, • peripheral edema, • rales, • jugular venous pulse, and • body weight. 	NYHA class (dyspnea at rest or on exertion) is a measure of patient symptom severity. The other measures reflect congestion (fluid retention). Both symptom improvement and decongestion (which is related to symptoms) reflect important therapeutic goals.
To compare the effects on all-cause mortality or Hospital readmission for HF through day 91	
 • Death from any cause to days 31 and 91 • Readmission for HF or death to days 31 and 91 • HF re-admission through days 31 and 91. 	HF readmission and death are outcomes representing disease progression. The composite is a generally accepted endpoint in AHF trials.
To support findings of primary analyses and to suggest further hypotheses for later research.	Requirement for treatment with intravenous vasopressors, inotropes, and/or mechanical ventilatory, renal or circulatory support or death from randomization through day 7 (“treatment failure”).	These treatments represent therapeutic failure.
	Changes from randomization to day 7, and to day 31, in biomarker levels including brain natriuretic peptide	Natriuretic peptide levels reflect congestion, creatinine reflects renal function, and troponin reflects myocardial damage.

OBJECTIVES	ENDPOINTS	JUSTIFICATION FOR ENDPOINTS
	(BNP), NT-pro-BNP, creatinine and troponin.	Effective HF therapy may reduce congestion, increase renal function and reduce cardiac damage.
	Time to worsening heart failure through the earlier of day 7 or discharge.	WHF has been shown to be associated with longer hospital stay and increased risk of HF readmission and death.
	Length of stay in ICU through 30 days following randomization	Reducing time in intensive care is an important therapeutic goal.
	Length of initial hospitalization through 30 days following randomization	Reducing time in hospital is an important therapeutic goal.
	Days dead or in acute care (including all intensive acute care units) out of the first 30 days following randomization.	This endpoint is another way to assess reduction of time in intensive care.
	Days dead or in the hospital out of the first 30 days following randomization.	This endpoint is another way to assess reduction of time in hospital.
	Hospital readmission through days 31 and 91	All-cause readmission can provide further information re effects on admissions for only HF.

4 STUDY DESIGN

4.1 OVERALL DESIGN

CORTAHF is a parallel-group, comparative, open-label, randomised (1:1), controlled trial. Patients with a diagnosis of AHF in the ED or after emergency presentation to hospital will be screened and informed of the study. After signed consent, patients will be randomized into the control group (usual AHF treatment) or intervention group (usual AHF treatment + prednisone).

Prednisone will be given for 7 days. Patients will be assessed at days 2, 4 or at discharge if earlier, and at day 7 at hospital visit. If the patient has been discharged before day 7, a follow-up visit will be scheduled at day 7 for endpoints assessment followed by a scheduled hospital visit at day 31 and a telephone follow-up at day 91. Study drug will be dispensed for the patient to take home until day 7.

4.2 SCIENTIFIC RATIONALE FOR STUDY DESIGN

A double-blind design would be preferred to the open-label design, but prohibitively expensive given available resources. The primary outcome, as well as the clinical outcomes including rehospitalization and death, are objective measures which should not be subject to overt bias.

4.3 JUSTIFICATION FOR DOSE

Oral “burst” of steroids are used and recommended in acute respiratory disease such as COPD or asthma exacerbation, or COVID-19. Recommended dose for burst is 40 mg prednisone once a day during 7 days.

4.4 END OF STUDY DEFINITION

A participant is considered to have completed the study if he or she has completed all phases of the study including the last visit or the last scheduled procedure shown in the Schedule of Activities (SoA), Section 1.3.

The end of the study is defined as completion of the last visit or procedure shown in the SoA in the trial globally.

5 STUDY POPULATION

5.1 INCLUSION CRITERIA

In order to be eligible to participate in this study, an individual must meet all of the following criteria:

1. Age 18 to 85 years of age
2. Unplanned ED visit or hospital presentation within the 12 hours prior to Screening with acute or worsening dyspnea and/or orthopnea, and pulmonary congestion on chest X-ray or lung ultrasound.
3. All measures from presentation to randomization of systolic blood pressure ≥ 100 mmHg, and of heart rate ≥ 60 bpm.
4. Written informed consent to participate in the study.
5. Biomarker levels indicative of congestion and inflammation: At Screening, NT-proBNP $> 1,500$ pg/mL and CRP > 20 mg/L
6. The patient agrees for follow-up visits at the the hospital at day 7 in case of earlier discharge and Day 31.

14. Participation in another intervention trial in the past 30 days
15. Anticipated non-adherence to study protocol or follow-up.
16. Pregnant or nursing (lactating) women.
17. Known hypersensitivity to steroids or constituents of prednisone tablets (excipients)
18. Psychotic states not yet controlled by treatment
19. Concomitant administration of live vaccines and up to 3 months after end of corticotherapy administration.
20. Patient under legal protection measure (tutorship or curatorship) and patient deprived of freedom
21. Persons subject to psychiatric care without their consent

5.3 LIFESTYLE CONSIDERATIONS

Note prohibited medications in Section 6.5.2.

5.4 SCREEN FAILURES

Screen failures are defined as participants who consent to participate in the clinical trial but are not subsequently randomly assigned to the study intervention or entered in the study. A minimal set of screen failure information is required to ensure transparent reporting of screen failure participants, to meet the Consolidated Standards of Reporting Trials (CONSORT) publishing requirements and to respond to queries from regulatory authorities. Minimal information includes demography, screen failure details, eligibility criteria, and any serious adverse event (SAE).

Individuals who do not meet the criteria for participation in this trial may be re-screened and included if all eligibility criteria are met upon re-evaluation.

5.5 STRATEGIES FOR RECRUITMENT AND RETENTION

Patients will be screened and included in the ED or after emergency presentation to the hospital after informed consent is signed.

	Number of participants
Total number of participants to be randomized	120
Number of centers	5
Enrolment period (months)	12
Number of participants/center	24
Number of participants/center/month	2

6 STUDY INTERVENTION

6.1 STUDY INTERVENTION(S) ADMINISTRATION

6.1.1 Study Intervention Description

Prednisone 40 mg will be administered in tablets. Prednisone is a corticosteroid (also called steroidal anti-inflammatory drug). This medicine belongs to the pharmacotherapeutic class of glucocorticoids, systemic use.

This medicine is reserved for adults and children over 6 years old and over 20 kg.

This drug is used in many diseases, where it is used for its anti-inflammatory effect. Its action is useful in the treatment of many inflammatory or allergic conditions.

6.1.2 Dosing and Administration

Dosage: 40 mg once a day to be taken during 7 days (taken with or without meals).

6.2 PREPARATION/HANDLING/STORAGE/ACCOUNTABILITY

6.2.1 Acquisition and accountability

Hospital pharmacies will dispense the investigational drugs to the patient in accordance with the specific research prescription completed and duly signed by the investigator. Only one dispensation (for 7-day supply) will be needed per patient.

6.2.2 Formulation, Appearance, Packaging, and Labeling

Prednisone tablets available in the hospital pharmacy will be dispensed.

6.2.3 Product Storage and Stability

This medicinal product does not require any special storage precautions. The pharmacist is responsible for ensuring adequate storage conditions for drugs.

6.3 MEASURES TO MINIMIZE BIAS: RANDOMIZATION AND BLINDING

The randomization list will be generated by a central statistician. A centralized randomization will be implemented for the study. Patients meeting eligibility criteria will be randomized either to intervention group (usual care + prednisone) or control group (usual care). The randomization will be performed in a 1:1 ratio, stratified by center and block balanced. The block size will not be communicated to the investigators.

This will be an open-label study. No investigator will have access to the randomization scheme during the course of the study.

6.4 STUDY INTERVENTION COMPLIANCE

During hospitalization, the follow-up of the treatment is ensured by the investigative team in charge of the patient who will record the date and time of the administrations. If the patient is discharged before day 7, the patient should be asked to note the date and time of each dose taken.

6.5 CONCOMITANT THERAPY

6.5.1 Auxiliary medication

In both the investigational and comparator treatment groups, patients will be treated according to routine practice.

Therefore, products will be prescribed in both groups and administered in accordance with routine care. They will not be provided by the Sponsor.

6.5.2 Authorized and prohibited treatments

The co-prescription of furosemide, prednisone and nitrates derivatives with the following drugs is not recommended for patients:

- Sildenafil, tadalafil or vardenafil
- Acetylsalicylic acid (in anti-inflammatory doses \geq 1g per dose and/or \geq 3g per day)
- Potent CYP3A inhibitors
- Mifamurtide
- Lithium
- Ototoxic medication (glycopeptides such as vancomycin and teicoplanin, aminoglycosides, organoplatins and loop diuretics)
- Hypokalaemic drugs (hypokalaemic diuretics, alone or in combination, stimulant laxatives, glucocorticoids, tetracosactide and amphotericin B (IV route).)
- Hyponatraemic drugs (diuretics, desmopressin, antidepressants inhibiting the reuptake of serotonin, carbamazepine and oxcarbazepine.).

6.5.3 Rescue Medicine

Aside from the study treatment, the management of the patient is at the discretion of the treating physician. If there is a formal indication for further steroid therapy, the prednisone treatment can be given in the control group and recorded in the CRF, and in both groups even after day 7. All treatments necessary for the proper management of the patient's state in the ED/hospital and subsequent hospitalization are authorized.

7 STUDY INTERVENTION DISCONTINUATION AND PARTICIPANT DISCONTINUATION/WITHDRAWAL

7.1 DISCONTINUATION OF STUDY INTERVENTION

Several situations are possible:

- Temporary suspension of treatment: the investigator must document the reason for suspending and resuming the treatment in the participant's source file and the case report form (CRF)
- Premature discontinuation of treatment, but the participant remains enrolled in the study until the end of their participation
- Premature discontinuation of treatment and withdrawal from the study
- If, during the course of his/her participation in the study, the participant presents one of the following criteria, then the study treatment must be discontinued but the participant will continue to be monitored for the study.
 - Thrombo-embolism event
 - Fracture
 - Gastro-intestinal bleeding
 - altered consciousness, confusion or dementia, psychotic state,
 - vaccination, hypersensitivity reaction,
 - pregnancy, severe renal or hepatic impairment, or
 - uncontrolled hyperglycemia.

The investigator must:

- Document the reason(s)
- Collect the assessment criteria at the time of ending participation in the study, if the participant agrees
- Schedule a follow-up for the participant, particularly in case of a serious adverse event.

In the case of severe adverse events, the investigator must notify the sponsor and follow up the participant for 1 month following the premature discontinuation of treatment. The Sponsor will be notified immediately of any serious adverse event. The serious adverse event will be monitored until it is resolved.

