1.2 SCHEMA

1.3 SCHEDULE OF ACTIVITIES (SOA)

Assessment	Visit 1	Visit 2	Visit 3	Visit 4	Visit 5	Visit 6 Telephone Contact
	Inclusion and randomization, ≤ 12h after ED/hospital presentation	Day 2 ~24 hours after randomization	Day 4 ~72 hours after randomization, or discharge if earlier	Day 7 7 (+/-1) days after randomization	Day 31 30 (+/- 5) days after randomization	Day 91 90 (+/- 5) days after randomization
Eligibility	X					
Pregnancy test for women of childbearing age	X					
Medical history	X					
Chest X-ray/ lung US*	X					
ECG*	X					
Echocardiography†	X					
Concomitant medications	X	X	X	X	X	
NT-proBNP, Tn, CRP	X	X (CRP only)	X (CRP only)	X (CRP only)	X	
Local labs: Hgb, serum sodium, glucose, potassium and kidney function measures, WBC count, % lymphocytes, liver function	X	X§	X§	X	X	
Physical exam including vital signs and clinical HF assessment	X	X	X	X	X	
EQ-5D-5L	X			X	X	
Biobanking samples	X		X	X	X	
Randomization	X					
Study drug prednisone‡ or usual care	X (seven days of treatment for investigational arm only)					
Clinical outcomes	←-----X----->					X
Adverse events	<-----X----->					

*Non-study assessment considered standard of care required for study eligibility.

†Non-study assessment considered standard of care which should have been performed within 6 months prior to inclusion, including during the current admission.

‡In patients randomly assigned to active intervention.

§To be recorded if done per local practice, but not required.

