8.1.7 Laboratory assessments

Blood samples (plasma) for central laboratory assessment will be taken at Visit 1 prior to randomization, at 72 hours and day 7 (\pm 1 day) as well as day 31. Samples will be collected in EDTA sample collection tubes and handled as described in the study's Laboratory Procedures manual. Sample aliquots will be stored frozen locally until shipped for longer-term storage and analysis. Unused samples will be discarded within 5 years after the study's completion.

Other lab assessments will be made according to local clinical practice. This should include at a minimum hemoglobin, WBC count, lymphocyte count, sodium, potassium, glucose, liver and kidney

function tests before randomization, day 7 (\pm 1 day), as well as day 31. Any assessments done at 24 hours (day 2) and/or 72 hours (day 3) should be recorded but are not required.

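### Uncontrolled hyperglycemia is a mandatory stop for prednisone, but no protocol-required glucose falls between baseline and Visit 4, when at most 1 or 2 of the 7 doses are left

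*Protocol*

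**What the plan says.** Section 7.1 of the protocol lists events after which prednisone has to stop while follow-up continues: if "the participant presents one of the following criteria, then the study treatment must be discontinued". One listed event is "uncontrolled hyperglycemia", with no glucose threshold attached.

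Section 6.1.2 sets the regimen: "40 mg once a day to be taken during 7 days". Section 4.1 lets patients discharged early take the remaining supply home.

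The Schedule of Activities (section 1.3) places glucose in one row with the other local tests: "Local labs: Hgb, serum sodium, glucose, potassium and kidney function measures, WBC count, % lymphocytes, liver function". The row is required at Visits 1, 4 and 5. At Visits 2 and 3 it carries a footnote: "To be recorded if done per local practice, but not required". Section 8.1.7 agrees that results at 24 and 72 hours "should be recorded but are not required". Visit 4 is timed at "7 (+/-1) days after randomization".

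Other blood is drawn at Visit 3 in any case. The schedule has CRP and a biobank sample there, and section 8.1.7 says that the central-laboratory samples "will be taken at Visit 1 prior to randomization, at 72 hours and day 7".

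**The concern.** Hyperglycemia is an expected steroid effect that can be silent, and recognising a silent case takes a measurement. The protocol orders the drug stopped for it but requires no glucose while most of the course is still to come. A patient who has no symptoms and no glucose test in usual care could take nearly all seven doses before a required value shows the problem.

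Three features of the design add to this. None of the 21 exclusion criteria concerns diabetes or baseline glucose. Dosing can continue at home, and the schedule has no contact between Visit 3 (which may be an early discharge) and Visit 4. The trial is open-label, so optional testing may be done more often in one arm than in the other, which would make hyperglycemia rates hard to compare in the adverse-event tables.

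What is at stake is patient safety in the prednisone arm and, to a lesser degree, the safety comparison. The CRP endpoint, its power and the secondary analyses do not depend on it.

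**Working it through.** The protocol states no figure of its own on this point, so the check is a count of doses and days.

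**Inputs**
- Seven doses, one a day (6.1.2).
- The day of randomization is study day 1 (day-numbering convention in the summary of changes).
- First dose on study day f. I take f = 1, which fits the Schedule of Activities but is an assumption; f = 2 is the sensitivity case.
- Visit 4 under the Schedule of Activities: 6 to 8 days after randomization, i.e. study days 7 to 9.
- Visit 4 laboratory tests under 8.1.7, if its day 7 ± 1 is read as study days: days 6 to 8.
- Visit 3: study day 4, or discharge if earlier.

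**Formula.** Doses left on study day d, before that day's dose: max(0, 7 − (d − f)). If that day's dose has already been taken, subtract one (not below zero).

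**Doses left at the first required glucose, before that day's dose**

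| Reading of Visit 4 | f = 1 | f = 2 |
|---|---|---|
| Schedule of Activities, days 7, 8, 9 | 1, 0, 0 | 2, 1, 0 |
| 8.1.7, days 6, 7, 8 | 2, 1, 0 | 3, 2, 1 |

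With f = 1, a required value can spare at most 1/7 = 14% of the course, or 2/7 = 29% on the 8.1.7 reading.

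**Time without a required glucose.** From day 1 to days 7–9 is 6 to 8 days, with no required test in between.

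**With a required value at Visit 3 (f = 1)**
- On day 4: 7 − 3 = 4 doses left before that day's dose, or 3 after it, so 57% or 43% of the course could be spared.
- At discharge on day 2: 6 or 5 doses left.
- The untested interval splits into 3 days, then 3 to 5 days (day 4 to days 7–9). After discharge on day 2 the second part is 5 to 7 days.

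**What cannot be computed.** The protocol gives no rate of hyperglycemia, of early discharge, or of usual-care glucose testing. The number of patients who would be missed is therefore not estimated.

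**The case against.** The strongest reply is that the rule is driven by events, not by a testing schedule. It stands beside fracture, gastrointestinal bleeding and confusion, which have no scheduled screening test either. The written schedule still offers several ways to notice the problem: examination at Visits 2 and 3, adverse-event questioning at each visit and standard-of-care laboratory values (8.2), and a check for steroid side effects at every visit (8.3.7). The treating physician has a baseline glucose and full discretion over management. The laboratory tests were made optional on purpose in version 2.0, to save burden and cost.

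Most of this stands. A reader might infer that the schedule as written cannot trigger the stop in time, or that 7.1 and 1.3 contradict each other. The documents support neither reading, because each of the routes above can trigger the stop. It is also correct that *uncontrolled* suggests hyperglycemia that has resisted management, so one raised value would not by itself meet the criterion.

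Some of the concern remains. Questioning and examination find symptomatic cases, not silent ones. The special-attention list in 8.3.7 names infection, thromboembolism, fracture and gastrointestinal bleeding, but not hyperglycemia. The stated reason for making the tests optional covers burden, cost and the main study objectives; it does not mention the stop rule. Kidney and liver tests are just as optional at these visits, and severe renal or hepatic impairment is on the same stop list; this point makes no claim about them.

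**Conclusion.** The point holds in a limited form and is worth considering; it is not an error that undermines the trial. No protocol-required glucose falls between baseline and Visit 4. By then at most 1 of 7 doses remains under the Schedule of Activities, or 2 under the study-day reading of 8.1.7, assuming a first dose on the day of randomization and no interruption of treatment. A start on day 2 adds one dose to each figure.

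The patients affected are those with asymptomatic hyperglycemia who have no glucose test in usual care. How many there are cannot be derived from the protocol, so neither a large nor a negligible safety effect can be asserted. The primary endpoint and power are unaffected.

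**What to change.** In sections 1.3 and 8.1.7, require one local glucose at Visit 3 (day 4, or discharge if earlier) and leave the rest of the day 2 and day 4 panel optional. Both arms are preferable, so that hyperglycemia is looked for equally; the prednisone arm is the minimum. Name the visit rather than the day, because 8.1.7 calls the 72-hour time day 3 and the Schedule of Activities calls it day 4.

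State that a raised value prompts management and repeat testing, and that prednisone stops if the hyperglycemia proves uncontrolled. Add hyperglycemia to the special-attention list in 8.3.7.

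Cost: at most 60 tests (prednisone arm) or 120 (both arms), with no new visit and at an existing blood draw. The protocol does not say whether an existing tube would serve, so one extra tube may be needed. By item count, the optional panel is 8 items × 2 visits = 16 item-visits per patient; one is given back, 1/16 = 6%, or about 3% overall if only one arm is tested. This counts items, not money or effort.

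Limit: cases that arise after Visit 3 still wait until Visit 4, including those in patients taking the drug at home after an early discharge.
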